7.4.3.2 Criteria to Resume Cabozantinib Treatment

Participants may resume treatment with cabozantinib when the drug-related AE(s) resolve to Grade \leq 1 or baseline value, with the following exceptions:

- Participants may resume dosing in the presence of Grade 2 fatigue
- Participants who delayed dosing due to prolonged QTcF may resume dosing at one reduced dose level once QTcF returns to \leq 500 msec
- Participants who delayed dosing due to UPCr $>$ 2.0 or urine dipstick protein \geq 3+ or urine protein $>$ 2.0 g / 24 may resume dosing at one dose level reduction when UPCr is \leq 2.0 or 24 hour urine protein \leq 2.0 g /24
- Participants who delayed dosing due to Grade 3 hypertension may resume dosing at the same dose or at one dose level reduction, at the discretion of the investigator, when hypertension has improved to Grade \leq 2
- Participants who delayed dosing due to Grade 4 lipase or amylase abnormalities may resume dosing upon resolution to Grade \leq 2
- Participants who delayed dosing due to major surgery should not resume cabozantinib until complete wound healing has taken place. Following cabozantinib resumption, participants should be monitored for wound dehiscence, wound infections, and other signs of impaired wound healing.
- Participants who develop a pulmonary embolism and/or DVT should have study treatment interrupted until therapeutic anticoagulation is established. Treatment with cabozantinib may be resumed in subjects with pulmonary embolism or DVT if it is determined that the event is uncomplicated and that the subject is deriving clinical benefit from cabozantinib treatment and that anticoagulation does not place them at a significant risk that outweighs the benefit of resuming treatment per discretion of the investigator.
- Participants who delayed dosing due to \leq Grade 2 hemorrhage may resume dosing if bleeding is under control (recovered to at least Grade 1 level) and has a low risk of recurrence
- If treatment is delayed $>$ 6 weeks for any reason, the participant must be permanently discontinued from study therapy, except in cases where permission to resume treatment is granted by the BMS Medical Monitor or designee.

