7.4.3 Criteria to Resume Treatment

7.4.3.1 Criteria to Resume Nivolumab and Ipilimumab Treatment

Delayed doses of nivolumab and/or ipilimumab should be administered as soon as the participant meets criteria to resume treatment. If a dose has been delayed, the participant should not wait until the next scheduled dosing date.

Participants may resume treatment with study drug when the drug-related AE(s) resolve to Grade ≤ 1 or baseline value, with the following exceptions:

- Participants may resume treatment in the presence of Grade 2 fatigue.
- Participants who have not experienced a Grade 3 drug-related skin AE may resume treatment in the presence of Grade 2 skin toxicity.
- For participants with Grade 2 AST, ALT, and/or total bilirubin abnormalities, dosing may resume when laboratory values return to baseline and management with corticosteroids, if needed, has been completed.
- Drug-related pulmonary toxicity, diarrhea, or colitis, must have resolved to baseline before treatment is resumed. Participants with persistent Grade 1 pneumonitis after completion of a steroid taper over at least 1 month may be eligible for retreatment if discussed with and approved by the BMS Medical Monitor or designee.
- Drug-related endocrinopathies adequately controlled with only physiologic hormone replacement may resume treatment.
- If treatment is delayed > 6 weeks, the participant must be permanently discontinued from study therapy, except as specified in Section 8.1.1.

For Arm B participants who delay nivolumab and ipilimumab dosing after Cycle 1 or 2, both nivolumab and ipilimumab must be resumed on the same day when the criteria to resume treatment are met.

For Arm B participants who delay nivolumab and ipilimumab dosing after Cycle 3 due to any drug-related AE meeting dose delay criteria that does not resolve within 14 days or requires treatment with systemic corticosteroids, it is acceptable to omit Cycle 4 if the investigator feels that ipilimumab was the main cause of the toxicity requiring dose delay. In this situation, when the participant meets criteria to resume nivolumab, the participant may proceed to Cycle 5 and begin nivolumab monotherapy maintenance.

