8.1.1 Nivolumab and Ipilimumab Dose Discontinuation (Arms A and B)

CA2099ER Global Revised Protocol 01

Implementation of CA2099ER Global Revised Protocol 01 stops further randomization into Arm B. Participants previously randomized to Arm B continue with Arm B treatment and continue with Arm B clinical planned events, per protocol.

The assessment for discontinuation of nivolumab, ipilimumab, and cabozantinib should be made separately for each study drug. Although there is overlap among the discontinuation criteria, if

discontinuation criteria are met for one study drug but not the other(s), it may be acceptable to continue treatment with the study drug(s) that are not felt to be related the toxicity, as specified below. If the investigator considers the toxicity to be related to all study drugs or is unable to determine which of the study drug(s) in Arm A or Arm B are the cause of toxicity, then all study drugs in the treatment regimen should be discontinued, and the recommendations for management of toxicity related to all study drugs should be promptly initiated.

Nivolumab and/or ipilimumab treatment should be permanently discontinued for any of the following:

- Any Grade 2 drug-related uveitis, eye pain or blurred vision that does not respond to topical therapy and does not improve to Grade 1 severity within the re-treatment period OR requires systemic treatment
- Any Grade 3 non-skin, drug-related adverse event lasting > 7 days, or recurs with the following exceptions for laboratory abnormalities, diarrhea, colitis, neurologic toxicity, drug-related uveitis, pneumonitis, bronchospasm, hypersensitivity reactions, infusion reactions, and endocrinopathies:
 - Grade 3 drug-related diarrhea, colitis, neurologic toxicity, uveitis, pneumonitis, bronchospasm, myocarditis, hypersensitivity reaction, or infusion reaction of any duration requires discontinuation. NOTE: The diagnosis of colitis should be supported by findings on colonoscopy whenever possible.
 - Grade 3 drug-related endocrinopathies, adequately controlled with only physiologic hormone replacement do not require discontinuation. Adrenal insufficiency requires discontinuation regardless of control with hormone replacement.
 - Grade 3 drug-related laboratory abnormalities do not require treatment discontinuation except:
 - ◆ Grade 3 drug-related thrombocytopenia > 7 days or associated with bleeding requires discontinuation

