 - ◆ Any drug-related liver function test (LFT) abnormality that meets the following criteria require discontinuation:
 - Grade ≥ 3 drug-related AST, ALT or Total Bilirubin requires discontinuation*
 - Concurrent AST or ALT > 3 x ULN and total bilirubin > 2x ULN
- Any Grade 4 drug-related adverse event or laboratory abnormality (including but not limited to creatinine, AST, ALT, or Total Bilirubin), except for the following events which do not require discontinuation:
 - Grade 4 neutropenia ≤ 7 days
 - Grade 4 lymphopenia or leukopenia or asymptomatic amylase or lipase

- Isolated Grade 4 electrolyte imbalances/abnormalities that are not associated with clinical sequelae and are corrected with supplementation/appropriate management within 72 hours of their onset
- Grade 4 drug-related endocrinopathy adverse events, such as, hyper- or hypothyroidism, or glucose intolerance, which resolve or are adequately controlled with physiologic hormone replacement (corticosteroids, thyroid hormones) or glucose-controlling agents, respectively, may not require discontinuation after discussion with and approval from the BMS Medical Monitor or designee.
- Any event that leads to delay in dosing lasting > 6 weeks from the previous dose requires discontinuation, with the following exceptions:
 - Dosing delays to allow for prolonged steroid tapers to manage drug-related adverse events are allowed.
 - Dosing delays lasting > 6 weeks from the previous dose that occur for non-drug-related reasons may be allowed if approved by the BMS Medical Monitor or designee.

Prior to re-initiating treatment in a participant with a dosing delay lasting > 6 weeks, the BMS Medical Monitor or designee must be consulted. Tumor assessments should continue as per protocol even if dosing is delayed. Periodic study visits to assess safety and laboratory studies should also continue every 6 weeks or more frequently if clinically indicated during such dosing delays.

- Any adverse event, laboratory abnormality, or intercurrent illness which, in the judgment of the Investigator, presents a substantial clinical risk to the participant with continued nivolumab dosing.

Participants in Arm B who meet any of the discontinuation criteria above prior to Cycle 3 must discontinue both nivolumab and ipilimumab and may not receive nivolumab monotherapy maintenance.

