8.1.2 Cabozantinib Dose Discontinuation

Permanently discontinue cabozantinib for participants with any of the following:

- Any requirement for more than 2 cabozantinib dose reductions (ie, reduction to less than 20 mg every other day)
- Any Grade \geq 2 drug-related arterial thromboembolic events, including cerebrovascular ischemia, cardiac ischemia/infarction, peripheral or visceral arterial ischemia
- Any Grade \geq 3 drug-related hemorrhage
- Grade 4 hypertension or persistent Grade 3 hypertension despite optimal medical management and cabozantinib dose reduction
- Drug-related reversible posterior leukoencephalopathy syndrome

- Development of drug-related fistula or GI perforation
- Drug-related nephrotic syndrome
- Any drug-related liver function test (LFT) abnormality that meets the following criteria requires discontinuation:
 - AST or ALT > 8 x ULN.
 - Concurrent AST or ALT > 3 x ULN and total bilirubin >2 x ULN, consistent with potential drug-induced liver injury (see [Section 9.2.7](#)).
- Any Grade 4 drug-related adverse event or laboratory abnormality, with the following exceptions:
 - Grade 4 neutropenia ≤ 7 days
 - Grade 4 lymphopenia or leukopenia
 - Grade 4 amylase or lipase abnormalities that are not associated with symptoms or clinical manifestations of pancreatitis
 - Isolated Grade 4 electrolyte abnormalities that are not associated with clinical sequelae and are corrected with supplementation/appropriate management within 72 hours of their onset
- Any dosing interruption lasting > 6 weeks unless the BMS Medical Monitor or designee is consulted and agrees with the rationale for resuming therapy after a delay > 6 weeks. Note that tumor assessments should continue as per protocol even if dosing is interrupted.
- Any adverse event, laboratory abnormality, or intercurrent illness which, in the judgment of the Investigator, presents a substantial clinical risk to the participant with continued cabozantinib dosing.

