7.4.2 Modifications of Study Therapy

7.4.2.1 Dose Delays

Each nivolumab infusion or sunitinib dose may be delayed. A dose will be considered as actually delayed if the delay is exceeding 3 days (ie greater than or equal to 4 days from scheduled dosing date) for nivolumab. Reason for dose delay will be retrieved from CRF dosing pages. It is worth noting that during the two week mandatory washout period for sunitinib, a daily dose of 0 mg will be entered in the CRF pages, with corresponding reason for dose modification recorded as “No Change”.

If cabozantinib is given daily, a daily dose of 0 mg entered in the CRF pages will be considered as delay. If cabozantinib is given every other day, then a daily dose of 0 mg will be entered every other day in the CRF pages, with corresponding reason for dose modification recorded as “No Change”. If there are more than one 0 mg daily dose entered consecutively, then this will be considered as delay.

The following parameters will be summarized by treatment group:

- Number of subjects with at least one dose delayed, the number of dose delays per subject, the reason for dose delay and the length of dose delay.

Note that similar dose delay summary table for Arm A and Arm C will be summarized for all intermediate/poor risk treated subjects.

For Arm B, both nivolumab and ipilimumab can be delayed at the same cycle. A dose will be considered as actually delayed if the delay is exceeding 3 days (ie greater than or equal to 4 days from scheduled dosing date) for nivolumab and ipilimumab. Cabozantinib a daily dose of 0 mg entered in the CRF pages will be considered as delay. Similar table will be produced for Arm B

subjects previously randomized to Arm B continue with Arm B treatment and continue with Arm B clinical planned events, per protocol.

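### In Arm A, the 6-week delay limit stops one drug in one protocol section and all study therapy in another

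*Protocol*

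**What the plan says.** Four protocol passages set a 6-week limit for the Arm A drugs.

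- **Cabozantinib, Section 7.4.3.2 (resuming).** Once a delay passes 6 weeks, whatever the cause, this applies: "the participant must be permanently discontinued from study therapy, except in cases where permission to resume treatment is granted". Permission is for the Medical Monitor or designee to give.
- **Cabozantinib, Section 8.1.2 (discontinuation).** The list opens with "Permanently discontinue cabozantinib for participants with any of the following" and includes an interruption of more than 6 weeks, unless the Medical Monitor is consulted and agrees to resumption.
- **Nivolumab, Section 7.4.3.1 (resuming).** "If treatment is delayed > 6 weeks, the participant must be permanently discontinued from study therapy, except as specified in Section 8.1.1".
- **Nivolumab, Section 8.1.1 (discontinuation).** The list opens with "Nivolumab and/or ipilimumab treatment should be permanently discontinued for any of the following" and includes: "Any event that leads to delay in dosing lasting > 6 weeks from the previous dose requires discontinuation, with the following exceptions". The exceptions are prolonged steroid tapers and, with Medical Monitor approval, delays unrelated to study drug.

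Section 8.1.1 also sets a general principle: "The assessment for discontinuation of nivolumab, ipilimumab, and cabozantinib should be made separately for each study drug". Section 7.4.1 lets either drug be delayed without the other, and Section 7.4.2.2 provides for Arm A participants who stay on cabozantinib after nivolumab alone is stopped. In Section 5.1, discontinuing study therapy ends the Treatment stage and begins Follow-up, with no further study therapy given.

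**The concern.** The resume sections attach the stop to the participant's study therapy. The discontinuation sections attach it to the drug that was delayed. In Arm A these are different actions, because study therapy is two drugs. Two sites could each follow a mandatory instruction for identical participants and differ on whether the partner drug continues.

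The situation is foreseeable without any toxicity. Section 7.4.1.2 has cabozantinib held at least 28 days before major surgery, and Section 7.4.3.2 bars resumption until the wound has healed completely. Of the 42-day limit, at most 42 − 28 = 14 days then remain for healing.

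At stake are Arm A exposure, the time-to-treatment-discontinuation curve in SAP 7.5.6 (where a participant counts as an event once off study therapy), and SAP 7.6.3, which separates discontinuation of cabozantinib only, nivolumab only, and both. In the A-versus-C comparison the ambiguity can arise only in Arm A, because sunitinib is a single drug.

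**Working it through.** The plan has no figure to reproduce for the scope question, so the passages are set side by side.

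| Section | Drug delayed | Limit | What stops | Exception |
|---|---|---|---|---|
| 7.4.3.2 | cabozantinib | delay > 6 weeks | study therapy | Medical Monitor permission |
| 8.1.2 | cabozantinib | interruption > 6 weeks | cabozantinib | Medical Monitor agreement |
| 7.4.3.1 | nivolumab | delay > 6 weeks, no starting point | study therapy | refers to 8.1.1 |
| 8.1.1 | nivolumab | > 6 weeks from previous dose | nivolumab (and/or ipilimumab) | steroid taper; approved non-drug-related delay |

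**Scope, cabozantinib.** With permission, neither section stops anything. Without it, 7.4.3.2 read literally stops both drugs and 8.1.2 stops one. Section 7.4.3.2 does not refer to 8.1.2 on this point, so nothing says which prevails.

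**Scope, nivolumab.** The reference to 8.1.1 can be read in two ways. If it imports only the listed exceptions, the same conflict exists outside them. If it lets 8.1.1 govern the 6-week stop altogether, the conflict disappears.

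**Starting point, nivolumab (lesser point).** Inputs: a dosing interval of 14 days (Section 7.1) and a limit of 6 × 7 = 42 days. The criterion in 8.1.1 counts from the previous dose. Section 7.4.3.1 and the sentence in 8.1.1 on consulting the Medical Monitor give no starting point.

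- Counted from the previous dose, the limit is passed after day 42, which is a dose more than 42 − 14 = 28 days late.
- Counted from the scheduled date, it is passed when the dose is more than 42 days late, which is after day 14 + 42 = 56 from the previous dose.
- Difference: 56 − 42 = 14 days, that is days 43 to 56 after the previous dose.

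If 7.4.3.1 is counted from the scheduled date and no exception applies, then on days 43 to 56 section 8.1.1 stops nivolumab and 7.4.3.1 stops nothing. From day 57, 8.1.1 stops nivolumab and 7.4.3.1, read literally, stops both drugs. If 7.4.3.1 is counted from the previous dose, the starting points agree and only scope is in dispute. For daily cabozantinib the two ways of counting differ by 1 day, which is immaterial.

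**The case against.** The strongest reply is that the protocol already has a governing principle. Section 8.1.1 calls for drug-by-drug assessment and allows treatment to continue with a drug not thought to have caused the toxicity. Sections 7.4.1 and 7.4.2.2 and SAP 7.6.3 take the same view. On this reading, study therapy in 7.4.3.2 is loose drafting: the same bullet appears in 7.4.3.3 for sunitinib, where there is only one drug. This may well be how the wording arose. It does not settle the matter, because the permission in 8.1.1 to continue the partner drug is framed around toxicity, Section 5.1 uses study therapy for the whole regimen, and the instruction in 7.4.3.2 is mandatory.

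Four stronger readings are tempting, and the documents do not support them.

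- *A participant held for wound healing automatically loses both drugs under 7.4.3.2.* Medical Monitor permission lifts the stop in both 7.4.3.2 and 8.1.2. The sections part only when it is refused or not sought.
- *The protocol states two contradictory starting points for nivolumab.* It states one and elsewhere gives none. Section 8.1.1 itself uses the unanchored phrase after the anchored one, so shorthand is a natural reading. Counting from the scheduled date is borrowed from SAP 7.4.2.1, where "greater than or equal to 4 days from scheduled dosing date" defines a delay for exposure tables and is not a rule for sites. The steroid-taper and approved-delay exceptions narrow the 14-day band further.
- *One participant on one day could have to stop both drugs, one, or neither.* That needs 7.4.3.1 to be counted in both ways at once.
- *Primary PFS is biased.* Stopping a drug is neither an event nor a censoring reason. Tumor assessments continue after discontinuation (Section 9.1.2.1) and analysis is as randomized (Section 10.2). An effect through earlier subsequent therapy, where primary PFS is censored, is possible but unquantified.

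**Conclusion.** The scope conflict is in the text and is clearest for cabozantinib: for one trigger, 7.4.3.2 stops study therapy and 8.1.2 stops cabozantinib. It applies to Arm A participants whose cabozantinib is delayed more than 6 weeks without permission to resume. Its size is one drug stopped or two; how often it would arise cannot be derived from the documents. The nivolumab version is weaker because of the reference to 8.1.1.

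The missing starting point is a lesser drafting gap, worth 14 days only on the assumption that an unanchored delay is counted from the scheduled dose date.

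The conclusion rests on reading study therapy in 7.4.3.2 as Section 5.1 uses it. The consequences shown are for treatment conduct, exposure and discontinuation summaries in Arm A, not for the validity of the primary comparison. The passages should be reconciled; no view is taken here on which rule is right.

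**What to change.** Reconcile Sections 7.4.3.1 and 7.4.3.2 with 8.1.1 and 8.1.2. In each, name the drug that is permanently stopped when the 6-week limit is passed, and state what happens to the partner drug, including when the delay was not caused by toxicity. State one starting point for the nivolumab 6-week count wherever it appears: 7.4.3.1, the 8.1.1 criterion and its exceptions, and the consultation sentence in 8.1.1. The sponsor decides both the scope and the starting point. The cost is a few words in the affected sections, with no new procedures or data collection.

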7.4.3.3 Criteria to Resume Sunitinib Treatment

Within a cycle, missed doses of sunitinib should be skipped and not replaced. Participants should never be dosed during the 2-week off period of each 6-week cycle, even if treatment delays occurred earlier in the cycle and therapy is ready to be resumed. If treatment is delayed past the end of the 6-week cycle, the start of the next cycle should be delayed until treatment with sunitinib resumes.

Participants may resume treatment with sunitinib when the drug-related AE(s) resolve to Grade \leq 1 or baseline value, with the following exceptions:

- Participants may resume dosing in the presence of Grade 2 fatigue
- Participants who delayed dosing due to prolonged QTcF may resume dosing at one reduced dose level once QTcF returns to \leq 500 msec
- Participants who delayed dosing due to UPCr \geq 2.0 or urine dipstick protein \geq 3+ may resume dosing at one dose level reduction when 24 hour urine protein $<$ 2.0 g
- Participants who delayed dosing due to Grade 3 hypertension may resume dosing at the same dose or at one dose level reduction, at the discretion of the investigator, when hypertension has improved to Grade \leq 2
- Participants who delayed dosing due to Grade 4 lipase or amylase abnormalities may resume dosing upon resolution to Grade \leq 2
- Participants who develop a pulmonary embolism and/or DVT should have study treatment interrupted until therapeutic anticoagulation is established. Treatment with cabozantinib may be resumed in subjects with pulmonary embolism or DVT if it is determined that the event is uncomplicated and that the subject is deriving clinical benefit from cabozantinib treatment and that anticoagulation does not place them at a significant risk that outweighs the benefit of resuming treatment per discretion of the investigator.
- Participants who delayed dosing due to \leq Grade 2 hemorrhage may resume dosing if bleeding is under control (recovered to at least Grade 1 level) and has a low risk of recurrence
- If treatment is delayed $>$ 6 weeks for any reason, the participant must be permanently discontinued from study therapy, except in cases where permission to resume treatment is granted by the BMS Medical Monitor or designee.

7.4.4 Treatment of Nivolumab- or Ipilimumab-Related Infusion Reactions

Since nivolumab and ipilimumab contain only human immunoglobulin protein sequences, they are unlikely to be immunogenic and induce infusion or hypersensitivity reactions. However, if such a reaction were to occur, it might manifest with fever, chills, rigors, headache, rash, pruritus, arthralgias, hypotension, hypertension, bronchospasm, or other allergic-like reactions. Regardless of whether or not the event is attributed to the study drugs, all Grade 3 or 4 infusion reactions should be reported within 24 hours to the study BMS Medical Monitor or designee and reported as an SAE if it meets the criteria. Infusion reactions should be graded according to NCI CTCAE (Version 4) guidelines.

Treatment recommendations are provided below and may be modified based on local treatment standards and guidelines, as appropriate:

For Grade 1 symptoms: (mild reaction; infusion interruption not indicated; intervention not indicated):

- Remain at bedside and monitor participant until recovery from symptoms. The following prophylactic premedications are recommended for future infusions: diphenhydramine 50 mg (or equivalent) and/or acetaminophen/paracetamol 325 to 1000 mg at least 30 minutes before additional study drug administrations.

For Grade 2 symptoms: (moderate reaction required therapy or infusion interruption but responds promptly to symptomatic treatment (eg, antihistamines, non-steroidal anti-inflammatory drugs, narcotics, corticosteroids, bronchodilators, IV fluids); prophylactic medications indicated for ≤ 24 hours):

- Stop the study drug infusion, begin an IV infusion of normal saline, and treat the participant with diphenhydramine 50 mg IV (or equivalent) and/or acetaminophen/paracetamol 325 to 1000 mg; remain at bedside and monitor participant until resolution of symptoms. Corticosteroid and/or bronchodilator therapy may also be administered as appropriate. If the infusion is interrupted, then restart the infusion at 50% of the original infusion rate when symptoms resolve; if no further complications ensue after 30 minutes, the rate may be increased to 100% of the original infusion rate. Monitor participant closely. If symptoms recur, then no further study drug will be administered at that visit.
- For future infusions, the following prophylactic premedications are recommended: diphenhydramine 50 mg (or equivalent) and/or acetaminophen/paracetamol 325 to 1000 mg should be administered at least 30 minutes before study drug infusions. If necessary, corticosteroids (up to 25 mg of hydrocortisone or equivalent) may be used.

For Grade 3 or 4 symptoms: (severe reaction, Grade 3: prolonged [ie, not rapidly responsive to symptomatic medication and/or brief interruption of infusion]; recurrence of symptoms following initial improvement; hospitalization indicated for other clinical sequelae (eg, renal impairment, pulmonary infiltrates). Grade 4: Life-threatening; pressor or ventilatory support indicated):

- Immediately discontinue infusion of study drug. Begin an IV infusion of normal saline and treat the participant as follows: Recommend bronchodilators, epinephrine 0.2 to 1 mg of a 1:1000 solution for subcutaneous administration or 0.1 to 0.25 mg of a 1:10,000 solution injected slowly for IV administration, and/or diphenhydramine 50 mg IV with methylprednisolone 100 mg IV (or equivalent), as needed. Participant should be monitored until the Investigator is comfortable that the symptoms will not recur. Study drug will be permanently discontinued. Investigators should follow their institutional guidelines for the treatment of anaphylaxis. Remain at bedside and monitor participant until recovery of the symptoms.

In case of late-occurring hypersensitivity symptoms (eg, appearance of a localized or generalized pruritus within 1 week after treatment), symptomatic treatment may be given (eg, oral antihistamine or corticosteroids).

